## **Statement of Compliance**

This study will be conducted in accordance with the Code of Federal Regulations on the Protection of Human Subjects (45 CFR Part 46), any other applicable US government research regulations, and institutional research policies and procedures. The Principal Investigator will assure that no deviation from, or changes to the protocol will take place without prior agreement from the sponsor and documented approval from the Institutional Review Board (IRB), except where necessary to eliminate an immediate hazard(s) to the trial participants. All personnel involved in the conduct of this study have completed Human Subjects Protection Training.

## List of Abbreviations

AE	Adverse Event/Adverse Experience
FDAAA	Food and Drug Administration Amendments Act
CFR	Code of Federal Regulations
CRF	Case Report Form
CSOC	Clinical Study Oversight Committee
DCC	Data Coordinating Center
dDPP	Digital Diabetes Prevention Program
DHHS	Department of Health and Human Services
DSMB	Data and Safety Monitoring Board
FFR	Federal Financial Report
FWA	Federalwide Assurance
GCP	Good Clinical Practice
HIPAA	Health Insurance Portability and Accountability Act
ICF	Informed Consent Form
IRB	Institutional Review Board
ISM	Independent Safety Monitor
MOP	Manual of Procedures
N	Number (typically refers to participants)
NIH	National Institutes of Health
OHRP	Office for Human Research Protections
OHSR	Office of Human Subjects Research
PAMS	Personalized Automated Messaging System
PI	Principal Investigator
QA	Quality Assurance
QC	Quality Control
SAE	Serious Adverse Event/Serious Adverse Experience
SOP	Standard Operating Procedure
US	United States

CONFIDENTIAL

This material is the property of the NYU School of Medicine and NYU Langone Health. Do not disclose or use except as authorized in writing by the study sponsor Behavioral Intervention Template Version: 11 January 2019

## Protocol Summary

Title	A randomized controlled trial to study the effects of automated physician directed messaging on patient engagement in the digital diabetes prevention program
Short Title	
Brief Summary	
This study aims to understand the effects of the physician-directed personalized automated messaging systems (PAMS) on patient engagement in the digital diabetes prevention program (dDPP). The messages are tailored to patient engagement levels based on established engagement thresholds, which are based on the patient's use of the dDPP application. The system is designed to minimize work for providers by sending automated targeted messages to patients to potentially increase engagement, prevent onset of diabetes and improve clinical outcomes. The patients in the study are automatically nudged using a combination of text messaging and mychart messaging.
 
Using a mixed-methods design, this study will be completed in three phases. The first phase was a quality improvement project to observe user engagement behavior in the dDPP program, and user test messages to potentially impact their behavior. Phase 2 will be recruiting up to 40 prediabetic patients from two sites within NYU Langone Health to adapt and iterate on the workflow to refine the study intervention. In addition, we will be conducting interviews with providers to build a provider-facing dashboard to report their patients' engagement behaviors and health outcomes. For Phase 3, we aim to conduct a randomized control trial with 432 pre-diabetic patients, all of whom will be using the dDPP application, randomized to the control group or one of 2 intervention groups who receive automated targeted messaging through PAMS. In addition, we surveying providers to gather feedback on the provider-facing dashboard and other study components.

Phase	
Phase 1: Observational study for clinical workflow adaptation
 
Phase 2: Pilot testing in NYU Langone Health clinics
 
Phase 3: RCT in NYU Langone Health clinics

Objectives	
Primary Objective: To observe change in weight
 
Secondary Objective: To observe any change in clinical outcomes (hemoglobin A1c levels, BMI), diagnosis of diabetes and to assess impact of engagement messaging and user engagement scores

Methodology	
Phase 2: User testing, workflow adaptation
 
Phase 3: Randomized Control Trial

Endpoint	
Primary endpoint: weight (lb),
 
Secondary endpoint: hemoglobin A1c levels, BMI, steps per day, diagnosis of diabetes, engagement score based on dDPP data logs and lesson completions, and patient demographics, social determinants, and other baseline descriptive data

Study Duration	
Phase 2: 18 Months
 
Phase 3: 42 Months

Participant Duration	
18 months

Duration of behavioral intervention	
12 months

CONFIDENTIAL

This material is the property of the NYU School of Medicine and NYU Langone Health. Do not disclose or use except as authorized in writing by the study sponsor Behavioral Intervention Template Version: 11 January 2019

Population	Pre-diabetic adult patients at NYU Langone Health (phase 2 and phase 3) and providers for the pre-diabetic patients (phase 2)
Study Sites	NYU Langone Health Faculty Group Practice (FGP), NYU Langone Family Health Center (FHC)
Number of participants	Phase 2: 40 patient participants and 40 provider participants          Phase 3: 433 participants and 20-40 provider participants.
Description of Study Intervention/Procedure	
Phase 2: 40 patients will be recruited to be part of the study. Patient participants will be asked to enroll virtually into Noom and willing to receive text messages based on engagement levels in Noom from the study team. This pilot testing will examine impact on workflow, uncover usability issues, and identify optimization opportunities to be included before large-scale implementation.
 
Provider participants: The study team will be interviewing providers to understand useful components of a provider facing dashboard within the EHR which will display the study participants' adherence data and health outcomes based on the dDPP Noom application. Providers will also be asked to participate in workflow adaptation sessions and user testing sessions to examine impacts on workflow, usability issues, and potentially lead to additional refinements.
 
Phase 3: 432 patients will be recruited to be part of the study, with 144 randomized to control arm (dDPP only), and to one of 2 intervention arm (dDPP+messaging). Participants will be asked to enroll into Noom and willing to receive text messages based on engagement levels in Noom from the study team. Providers will be asked to participate in an exit survey to gather feedback on their experience with the provider facing dashboard and other study components.

Reference Therapy	N/A
Key Procedures	N/A
Statistical Analysis	
The primary analysis will follow the intention-to-treat framework.
 
For phase 2, we will assess usability of the engagement messages to the patients and address any research and technical issues to prepare for phase 3, and also do workflow analysis and adaptation for the provider-facing interface.
 
For phase 3, we will analyze the difference in means between the three arms in the RCT to assess impact of engagement messaging for our primary endpoint.

CONFIDENTIAL

This material is the property of the NYU School of Medicine and NYU Langone Health. Do not disclose or use except as authorized in writing by the study sponsor Behavioral Intervention Template Version: 11 January 2019

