#### 4.2.3 Exploratory Endpoints

## 5 Study Enrollment and Withdrawal

### 5.1 Inclusion Criteria

In order to be eligible to participate in this study, an individual must meet all of the following criteria:

Provider Inclusion Criteria: (a) Fulltime primary care provider (MD/DO, NP) practicing at the participating FHCs or FGPs and, (b) Provide care to at least five patients with a diagnosis of pre-diabetes.

Patient Inclusion Criteria:

In order to be eligible to participate in this study, an individual must meet all of the following criteria:

1. 18 years or older,  $BMI \geq 25 \text{ kg/m}^2$  ( $> 22 \text{ kg/m}^2$  if self-identified as Asian)
2. A diagnosis of prediabetes (either diagnosis of prediabetes or an HbA1C level of 5.7%-6.4% in past 18 months)
3. Baseline self-test a1c value of 5.4 to 6.4
4. Safe to engage in moderate physical exercise (as determined by their PCP)

CONFIDENTIAL

This material is the property of the NYU School of Medicine and NYU Langone Health. Do not disclose or use except as authorized in writing by the study sponsor Behavioral Intervention Template Version: 11 January 2019

5. Sufficient English to be able to complete the enrollment process
6. Has app capable device with data to use the dDPP application and receive text messages
7. NYU Langone Health Patient with assigned PCP on EPIC/EHR

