### **6.1.3 Assessment of Subject Compliance with Study Intervention**

Subject data will be captured and securely stored on NYULH enterprise supported Redcap. The study staff will send Redcap surveys at indicated time points to the study participants. The participants will be reminded twice to complete the survey via text message or redcap generated email. Additionally, study compliance will be assessed by reviewing ddpp-related engagement data and activity

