#### **Phase 3: RCT**

Once the intervention has been tested and refined in the NYU Langone clinics, the next phase of the study will be to recruit practices and patients for the full-scale clinical trial. The intervention will be rolled out to additional sites in a randomized control trial. The intervention patients will receive the dDPP, text messaging support and their providers will have access to the adapted dDPP-EHR tool suite from the previous two phases, while the control patients will only receive the dDPP via mobile application (not integrated into the EHR). The overall outcomes of this phase will be both clinical (i.e. weight reduction, physical activity, HbA1C levels) and engagement-related (i.e. patient engagement and perceived provider involvement).

The patient participants in Phase 3 will be randomized into intervention arm 1 or intervention arm 2 or control group. Those in the intervention group will receive text messages via their mobile smart phone. All participants will be part of the dDPP/ Noom program, and will be interviewed at baseline, 6 months, and 12 months over the course of the study. Participants randomized to intervention arm 2 will be given the option to choose the time of day they receive messages and frequency of reminder to use noom. Intervention arm 1 will not be given that option.

The provider participants in Phase 3 will receive requests to complete an exit survey where they will be queried about their experiences with the dashboard tool and other study components.

CONFIDENTIAL

This material is the property of the NYU School of Medicine and NYU Langone Health. Do not disclose or use except as authorized in writing by the study sponsor Behavioral Intervention Template Version: 11 January 2019

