## **10.2 Statistical Hypotheses**

Our primary hypothesis is that patients receiving the dDPP + the dDPP-EHR tool suite will have greater reduction in weight loss, greater increase in physical activity, and greater reduction in HbA1c.

Our secondary hypothesis is that patients receiving the dDPP + the dDPP-EHR tool suite will show higher engagement, assessed by number of logins and lessons completed. They will also report higher perceived provider involvement.

Our exploratory hypothesis posits that patients who engage more fully with the dDPP may engage in healthy behaviors more than those who are less engaged, which should lead to better weight loss outcomes. Hence, we hypothesize that patient engagement level can mediate the relationship between intervention and improvement in patient health outcome.

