## **10.3 Analysis Datasets**

Our primary analyses will use intention-to-treat (ITT) analysis dataset of all randomized participants. Participant baseline demographics and clinical characteristics will be collected. Repeated measurements of participant weight, physical activity, and HbA1c level at baseline, 6 and 12 months from baseline, and patient engagement and perceived provider involvement at 6 and 12 months from baseline will also be collected. Long-formatted data will be stored and analyzed.

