#### 10.4.2 Analysis of the Primary Efficacy Endpoint(s)

The table below outlines the study's main outcomes. Whenever possible, outcomes ascertained via automated or technology-facilitated objective approaches are used to enhance the pragmatic approach and minimize provider and patient burden; while weight and activity data will be collected more frequently (and be viewable to intervention patients and providers), 6- and 12- month assessments will be used to evaluate impact. To ensure data endpoint capture for weight and physical activity at 6 and 12 months, the study team will conduct outreach and troubleshoot with patients missing data at any of these intervals.

Construct	Measure	Data Source	Collected at (months)
Clinical outcomes	Weight reduction (kg)	Noom via wireless scale and survey, EHR	Baseline, 3, 6, 9, 12
	Physical activity (steps/day)	Noom via wireless pedometer	Baseline, 6, 12
	Hemoglobin A1C (%)	HbA1C home test kit and survey, EHR	Baseline, 6, 12
Engagement outcomes	Patient engagement (# dDPP logins) (# dDPP lessons completed)	Noom	6, 12
	Perceived provider involvement with dDPP progress	Patient portal 1-item survey	
Patient characteristics	Demographics, social determinants, and other baseline descriptive data	EHR	Baseline, 12

Change in body weight, a repeatedly measured continuous variable, will be our primary weight-based outcome. Secondarily, we will assess achievement of a 7% weight loss (the DPP weight goal), a binary outcome. Weight will be collected from the bluetooth linked wireless weight scale (Fitbit Aria or iHealth Fit/Nexus) that automatically reports weigh-ins to the Noom server. Mean steps per day, a repeatedly measured continuous variable, will be assessed using Fitbit or iHealth accelerometers integrated into the Noom platform. This objective device has been well-validated for the measurement of steps and found to be acceptable by study participants. HbA1C, the most common test used for prediabetes monitoring, will be assessed as a secondary outcome via HbA1C testing performed at home. HbA1C will be collected at baseline, 6 and 12 months. Patients will be sent a HbA1C testing kit upon enrollment, and prompted by

CONFIDENTIAL

This material is the property of the NYU School of Medicine and NYU Langone Health. Do not disclose or use except as authorized in writing by the study sponsor Behavioral Intervention Template Version: 11 January 2019

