#### **10.4.3 Analysis of the Secondary Endpoint(s)**

Secondary endpoint is patient engagement defined as dDPP utilization, which serves as the key mediator. Patient engagement will be measured using data on logins and lesson completion from the Noom platform, and perceptions of provider involvement. Mean logins and lesson completion are both continuous variables measured at 6 and 12 months from baseline. Patient perceived provider involvement will be measured using a single item survey inspired by validated patient satisfaction instruments and delivered via the NYU patient portal.

We will utilize a linear mixed-effect model or GEE to examine the association of intervention with patient engagement and associations of patient engagement with concurrent or lagged clinical outcomes, with practice as a random effect. If significant associations were found, we will explore the extent to which engagement with the program acts as a mediator. We posit that those who engage more fully with the dDPP may engage in healthy behaviors more than those who are less engaged, which should lead to better weight loss outcomes. Here, we propose using a single mediator causal model approach with bootstrap-derived confidence intervals to measure dDPP effect on weight loss through the specific mechanism of patient engagement.

We will also examine differences in primary outcomes and engagement measures using sex as a biological variable. Techniques used to deal with missing data and potential imbalance between treatment arms will be similar to that in the analysis of primary endpoints.

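### Perceived provider involvement is collected only through the patient portal, which eligibility does not require, with no reminder or back-up source for non-response

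*Combined protocol and SAP*

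**What the plan says.** **The outcome.** Section 10.2 includes it in the secondary hypothesis, with a direction: "They will also report higher perceived provider involvement". Section 10.3 sets the times: "patient engagement and perceived provider involvement at 6 and 12 months from baseline will also be collected". No baseline value is planned.

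**Its source.** The outcome table in 10.4.2 lists "Patient portal 1-item survey", and 10.4.3 describes a "single item survey inspired by validated patient satisfaction instruments and delivered via the NYU patient portal". Neither names a second source.

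**Access to the portal.** Section 5.1 asks for a device that can run the app and receive texts, and for "NYU Langone Health Patient with assigned PCP on EPIC/EHR". No criterion concerns a portal account. Section 2.3.1 expects patients to use MyChart, which I take to be the portal, although the documents do not say so outright. Onboarding (6.1.1, 7.3.2) covers Noom, the tracker and the scale, with no portal step. MyChart is the usual first recruitment contact (5.4, 7.3.1), but the Schematic and 5.4 also provide for phone, email and in-person recruitment.

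**Other surveys.** Section 6.1.3 says "The study staff will send Redcap surveys at indicated time points to the study participants", with two reminders by text or email.

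**Missing data.** Section 10.4.3 carries over the approach of 10.4.2, weighted GEE under missing at random. EHR extraction fills in only HbA1c and weight, and the planned outreach covers only weight and physical activity.

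**Intervention channel.** The Brief Summary says "The patients in the study are automatically nudged using a combination of text messaging and mychart messaging". For phase 3, section 7.1 says "Those in the intervention group will receive text messages via their mobile smart phone".

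**The concern.** The item reaches only patients who hold and use a portal account, and the plan neither requires nor sets up that account. Patients in closer touch with their practice may be more active in the portal, and closeness to the provider is near to what the item asks about. The trial is unblinded (10.6.1). Only intervention patients receive the messages and have providers with dashboard access (6.1), so portal use might rise in those arms alone.

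If response depends on arm and answer together, the comparison among responders can show a difference that is not there or hide one that is. At stake is the trial's only patient-reported test of whether the tool suite makes providers seem more involved, which is central to the rationale in 2.2.

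**Working it through.** **1. The plan's own figure.** There is none for this outcome. The only design calculation is power for weight. With 2 kg, SD 5 kg and 200 per arm, 2 / (5 × √(2/200)) = 4.0 and Φ(4.0 − 1.96) = 97.9%, against 97% stated. It agrees and has no bearing on this item.

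**2. When non-response biases the comparison.** Assume a yes/no item (the documents give no response scale). Let p be the true proportion answering yes, and r1 and r0 the response probabilities of those who would say yes and no. The proportion seen among responders is

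q = p·r1 / (p·r1 + (1 − p)·r0).

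This depends on response only through the ratio r1/r0. With no true effect:
- response differs by arm but not by answer: r1/r0 = 1 in each arm, so q = p and there is no bias;
- response depends on the answer equally in each arm: q is wrong by the same amount in each, so the difference is zero;
- r1/r0 differs between arms: the difference is spurious.

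**3. Illustration.** The 1:2 allocation of 432 (10.4.1) gives 144 control and 288 intervention patients. There is no true effect, and a pooled two-proportion test is used at two-sided 0.05. All values of p and all response rates are assumed.

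| True yes | Control r1/r0 | Intervention r1/r0 | Spurious difference (points) | False-positive rate |
|---|---|---|---|---|
| 50% | 60%/60% | 80%/80% | 0 | 5% |
| 50% | 80%/60% | 80%/60% | 0 (both seen as 57%) | 5% |
| 50% | 60%/60% | 70%/60% | +3.8 | 9% |
| 50% | 60%/60% | 80%/60% | +7.1 | 20% |
| 50% | 60%/60% | 90%/60% | +10.0 | 36% |
| 40% | 50%/50% | 65%/50% | +6.4 | 15% |
| 40% | 50%/50% | 80%/50% | +11.6 | 38% |
| 40% | 60%/40% | 70%/70% | −10.0 | 31% |

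Rows at 50% use the normal approximation and rows at 40% use 40,000 simulations. At a true level of 30%, the third to fifth rows become +3.3, +6.4 and +9.1 points with 8%, 17% and 31%.

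Fourth row in full: q in the intervention arms is 0.5 × 0.80 / (0.5 × 0.80 + 0.5 × 0.60) = 0.40 / 0.70 = 57.1%, against 50.0% in control. Responders number 288 × 0.70 = 201.6 and 144 × 0.60 = 86.4.

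Last row: control 0.24 / (0.24 + 0.24) = 50%, intervention 0.28 / (0.28 + 0.42) = 40%.

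**4. Does the planned analysis cover it?** Weighting under missing at random can allow for response explained by arm and by observed data. It cannot correct response that still depends on the unobserved answer. A patient who never answers has no baseline or other value of this item on which to base a weight. No sensitivity analysis for that case and no report of response by arm is planned.

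**5. Is MyChart a treatment channel?** One Brief Summary sentence, covering all phases, says so. The intervention description in the same Summary, 4.1, the phase 3 parts of 6.1 and 7.1, and 7.3.3.2 describe texts. Section 6.1.1 has delivery online and by text, without naming MyChart. In phase 2, section 6.1 gives MyChart a correspondence role, with email as the alternative. These passages need reconciling, but steps 2 to 4 hold either way.

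**The case against.** **MyChart as treatment.** From the Brief Summary a reader might infer that portal messages are part of treatment, so that intervention patients are drawn to the portal by design. The operational sections do not support this: for phase 3 they name texts and not MyChart. Section 2.3.1 expects MyChart use by patients generally, with no restriction by arm.

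**Responders and randomised groups.** A reader might also infer that the responders are known to differ from the randomised groups. No activation or response rate appears anywhere, and the link between portal use and provider contact is plausible but undocumented. The table shows what could happen. It rests on an assumed binary item and a simpler test than the planned mixed model or GEE, and its inputs can produce either sign.

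**Importance.** The item is in 10.2 and 10.4.3 but not in the endpoint lists (Summary, 4.2.2) or the secondary objectives (3.2). Portal delivery suits the low-burden approach of 10.4.2. Follow-up visits also ask about the patient-provider relationship (7.3.3.2), which offers a rough cross-check in all arms, though it is not the same item.

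**The remedy.** REDCap response is voluntary too, and its reminders may go by text, which is the treatment channel. Section 15.3 pays for the 6- and 12-month surveys without limiting this to REDCap, so the portal item is not shown to be unpaid.

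All of this stands as a limit on the size and certainty of the point. It leaves in place a single source with no access requirement, no described reminder and no back-up, and an analysis that does not cover answer-dependent response.

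**Conclusion.** The point holds as a limited, inexpensive improvement. Portal-only collection leaves room for selective non-response on one outcome in the secondary hypothesis, and the planned weighting would not correct response that depends on the unobserved answer. Bias needs dependence on arm and answer together; with no true effect, either alone leaves the arm difference at zero.

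Size and direction cannot be computed from the documents. Under the assumed rates above, spurious differences run from −10.0 to +11.6 points, with false-positive rates up to 38%; these are not estimates for this trial. The conclusion assumes that the NYU patient portal is MyChart or a similar account-based system. It does not assume that MyChart carries the intervention. The primary weight outcome is unaffected.

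**What to change.** - In the 10.4.2 table and in 10.4.3, collect the item within the 6- and 12-month REDCap surveys sent to all three arms.
- Use the same reminders in every arm, by REDCap email where possible, because text is the treatment channel.
- Report the item's response rate by arm at 6 and 12 months.
- Flag the mode of any answers already given through the portal.
- Reconcile the Brief Summary with the Summary's intervention description, 4.1, 6.1, 6.1.1, 7.1 and 7.3.3.2 on whether MyChart messages are part of the phase 3 intervention.

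The cost is protocol wording and one question moved into an existing survey, with no added visit. The downsides are mixed modes for answers already collected and some remaining non-response, which the change should reduce but will not remove.
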